## CLINICAL TRIAL PROTOCOL SYNOPSIS

Name of company: Boehringer Ingelheim		Tabulated Trial Protocol	
Name of finished product: Giotrif® / Gilotrif®, Afatinib			
Name of active ingredient: BIBW 2992			
Protocol date: 15 Nov 2011	Trial number: 1200.125		Revision date: 24 June 2016
Title of trial:	LUX-Lung 8: A randomized, open-label Phase III trial of afatinib versus erlotinib in patients with advanced squamous cell carcinoma of the lung as second-line therapy following first-line platinum-based chemotherapy		
Co-ordinating Investigators:			
Trial sites:	Multi-center trial		
Clinical phase:	III		
Objectives:	
Primary: Compare efficacy of afatinib with erlotinib as second-line treatment for patients with squamous cell carcinoma of the lung, as measured by progression-free survival (PFS).
 
Key secondary: Compare overall survival (OS) in both treatment groups
 
Secondary: Objective response rate (ORR), disease control rate (DCR), tumour shrinkage and the assessment of Health-related Quality of Life (HRQoL) and safety in both treatment groups
		
Methodology:	Randomised, open-label, active control study comparing afatinib vs. erlotinib. Eligible patients will be randomized to receive either afatinib or erlotinib in a 1:1 ratio. Independent assessment of the primary endpoint will be completed in a treatment-blinded manner. Randomization will be stratified based on race (Eastern Asian vs. non-Eastern Asian).		
No. of patients:			
total entered:	795		
each treatment:	Afatinib: 398 Erlotinib: 397		
Diagnosis :	Patients with diagnosis of advanced NSCLC squamous or mixed histology, who have completed at least 4 cycles of platinum-based doublet chemotherapy and who are eligible to receive 2 nd line therapy.		

Proprietary confidential information.

© 2016 Boehringer Ingelheim International GmbH or one or more of its affiliated companies. All rights reserved.

This document may not - in full or in part - be passed on, reproduced, published or otherwise used without prior written permission.

Name of company: Boehringer Ingelheim		Tabulated Trial Protocol	
Name of finished product: Giotrif ® / Gilotrif ® , Afatinib			
Name of active ingredient: BIBW 2992			
Protocol date: 15 Nov 2011	Trial number: 1200.125		Revision date: 24 June 2016
Main criteria for inclusion:	
 
• Diagnosis of advanced stage NSCLC considered to be squamous histology, including mixed histology, in the opinion of the investigator.
 
• Eligible for EGFR-directed therapy in 2nd line setting.
 
• Measurable disease according to RECIST 1.1.
 
• Eastern Cooperative Oncology Group (ECOG) score: 0 or 1.
 
• Availability of tumour tissue material for correlative studies. Archived tumour tissue is acceptable.
 
• Adequate organ function.
 
• No prior treatment with EGFR directed small molecules or antibodies.
 
		
Test products:	Afatinib (BIBW 2992)		
dose:	Starting dose 40 mg once daily. Escalation to 50 mg/day at beginning of Course 2 in patients meeting specified safety and compliance criteria. Dose reduction to 40 (if applicable), 30, and 20 mg/day in the presence of drug-related adverse events.		
mode of admin.:	Oral		
Comparator products:	Erlotinib		
dose:	Starting dose of 150 mg once daily. Dose reduction to 100 and 50 mg/day in the presence of known drug-related adverse events.		
mode of admin.:	Oral		
Duration of treatment:	Until patient experiences disease progression, according to RECIST 1.1.		

Proprietary confidential information.

© 2016 Boehringer Ingelheim International GmbH or one or more of its affiliated companies. All rights reserved.

This document may not - in full or in part - be passed on, reproduced, published or otherwise used without prior written permission.

Name of company: Boehringer Ingelheim		Tabulated Trial Protocol	
Name of finished product: Giotrif ® / Gilotrif ® , Afatinib			
Name of active ingredient: BIBW 2992			
Protocol date: 15 Nov 2011	Trial number: 1200.125		Revision date: 24 June 2016
Criteria for efficacy:	
The primary endpoint of this study is progression-free survival, as determined by RECIST 1.1.
 
Key Secondary endpoint:
 
 
• Overall survival
 
 
Secondary endpoints of this trial are:
 
 
• Objective response (CR, PR) according to RECIST 1.1
 
• Disease control (CR, PR, SD) according to RECIST 1.1
 
• Tumour shrinkage
 
• Health-related Quality of Life (HRQoL)
 
		
Criteria for safety:	
Safety of afatinib and erlotinib will be evaluated by intensity and incidence of adverse events, graded according to NCI CTCAE version 3.0, including:
 
 
• The overall incidence and intensity of adverse events
 
• Gastrointestinal events (vomiting, nausea, diarrhoea)
 
• Skin reactions (rash, acne)
 
 
Tolerability of afatinib and erlotinib will be assessed based on dosage reductions and discontinuation due to adverse events.
		


Statistical methods: The primary analysis will compare afatinib vs erlotinib in terms of progression-free survival (PFS). The randomised treatment regimens will be compared using a log-rank test stratified by race (Eastern Asian vs non-Eastern Asian). A stratified Cox proportional-hazards model will be used to derive the hazard ratio and 95% confidence interval (CI) between the two regimens. Kaplan-Meier estimates and 95% CI will be calculated at landmark time points. Three hundred seventy-two PFS events would be expected to provide 90% power for the log-rank test, assuming a hazard ratio of 0.714 for afatinib relative to erlotinib (corresponding to median times of 14 vs 10 weeks, respectively) with two-sided <math>\alpha = 0.05</math>.
 
An interim analysis will be performed after at least 300 patients have been randomized and when 130 patients have experienced PD, as determined by assessment at the study sites, among the first 176 patients randomized into the trial. The analysis will be reviewed by the DMC and will result in one of the following decisions: 1.) No change in planned accrual, 2.) partial curtailment of accrual, or 3.) stop of accrual.
 
Overall survival (OS) is a key secondary endpoint. The analysis of OS will estimate the hazard ratio and the corresponding 95% confidence interval based on a Cox-PH model. Additionally, a stratified log-rank test will be performed. Kaplan-Meier estimates of OS will be tabulated. 632 deaths would be expected to provide 80% power for log-rank test, presuming a hazard ratio of 0.800 for afatinib relative to erlotinib (corresponding to median survival times of 8.75 vs. 7.00 months, respectively) with two-sided <math>\alpha = 0.05</math>.
 
OS will be analysed twice. The first analysis will be performed at the time of the primary PFS analysis using a Haybittle-Peto stopping boundary for efficacy (p-value <0.0001). The primary analysis of survival is planned at 632 deaths. However, if the futility analysis curtails accrual at 500 patients, the primary analysis of OS will be performed after 80% of the randomized patients have died.
			

Proprietary confidential information.

© 2016 Boehringer Ingelheim International GmbH or one or more of its affiliated companies. All rights reserved.

This document may not - in full or in part - be passed on, reproduced, published or otherwise used without prior written permission.

## FLOW CHART

Visit	Screening	Course 1		Course 2 and subsequent courses*	End of treatment **	Follow-up	Observation Period
Visit Abbreviation	SCR	C1V1	C1V2	CxV1 a	EOT	FUP	OPy b
Day	Up to 28 days before treatment	Day 1 ***	Day 8 (± 2 days)	Day 1 of each course (- 3 to +2 days) ****	0-7 days after permanent discontinuation of study drug	28 Days after discontinuation of study drug (+ 7 days)	Every 28 Days (± 7 days) after FUP
Informed consent	X						
Tumour sample shipment 		X					
Demographics	X						
Medical history	X						
Complete Physical exam 	X				X		
Clinical Assessment 		X	X	X		X	
Vital signs	X	X	X	X	X	X	
Performance status	X	X		X	X	X	
ECG (as indicated) 	X		X	X 	X		
Safety laboratory tests 	X	X		X	X	X	
Pregnancy Test	X	X			X		
ECHO or MUGA 	X			X 	X 		
Review of in-/exclusion criteria	X	X					
Randomization		X					
Collection of blood for Biomarker analysis 		X		X	X		
Patient-reported outcomes 		X		X 	X	X	
Adverse event evaluation 		X-----X					
Concomitant therapy	X	X-----X					
Tumour assessments 	X	Tumour assessments are completed at weeks 8, 12, 16, and every 8 weeks thereafter. After approval of protocol version 3, assessments to be performed every 18 weeks unless clinically indicated.					
Treatment Adherence Check 			X	X	X		
Dispense Trial Drug		X		X			
Termination of trial medication					X		
IXRS	X	X		X	X		
Collection of Vital Status 							X

Proprietary confidential information.

© 2016 Boehringer Ingelheim International GmbH or one or more of its affiliated companies. All rights reserved.

This document may not - in full or in part - be passed on, reproduced, published or otherwise used without prior written permission.

\* All courses are 4 weeks in duration (28 days). Patients may continue on treatment for unlimited courses, until the criteria for stopping medication are met (see [Section 3.3.4.1](#)).

\*\* If the decision to permanently discontinue study drug is taken during a scheduled visit, the EOT visit should be performed instead of the scheduled visit.

\*\*\* Randomization into the study via the IXRS is permitted up to 2 days prior to the C1V1 if site procedures require advance randomization to accommodate the logistics of dispensing study medication to patients. Sites that use this option must include a copy of this policy in the ISF and submit a copy to the sponsor.

\*\*\*\* Except as noted for ECHO or MUGA and tumour assessments

ax is the course number in CxV1

by is the visit number in Opy

1. Randomization into study does not need to be delayed for shipment of tumour sample; however, availability of tumour sample for shipment to central laboratory must be confirmed prior to randomization and shipped within 28 days of randomization.
2. Includes height (at screening only) and weight.
3. Limited physical examination to capture clinical assessment of ongoing or new adverse events and monitor for signs and symptoms of clinical response.
4. A 12-lead resting digital electrocardiogram (ECG) will be performed at Screening to establish a baseline assessment, at C1V2 (Day 8 of treatment), at the start of every third course thereafter (C4, C7, etc.) and EOT. After approval of Protocol Version 3.0, ECG will only be performed if clinically indicated.
5. Includes hematology, serum biochemistry, and urinalysis. Refer to the Investigator Site File (ISF).
6. ECHO or MUGA (At German sites, only ECHO is allowed) will be performed during screening, at Course 4 and then at every third course (Course 7, 10, 13 etc.), and at EOT (if not performed in the previous 8 weeks). Requirement for EOT ECHO or MUGA may be waived for patients meeting all of the following criteria: 1) too sick from their disease or disease related symptoms to travel in the opinion of the investigator, 2) have had evidence of stable LVEF on the previous scheduled post treatment assessment and 3) have no evidence of cardiovascular disease. For LVEF evaluations, the assessment can occur  $\pm 7$  days of the scheduled Day 1 of the corresponding course.  
After approval of Protocol Version 3.0, ECHO or MUGA will only be performed if clinically indicated.
8. Blood sample will be collected and plasma will be sent to logistics laboratory at baseline (C1V1), C2, and at EOT or determination of disease progression. After approval of Protocol Version 3.0, the collection of blood sample at EOT will no longer be required.
9. [EQ-5D](#), [EORTC QLQ-C30](#) and [EORTC QLQ LC-13](#) questionnaires will be completed at baseline and then (before seen by the investigator) at the start of course 2, 3, 4, and every 2nd course thereafter, EOT and FUP. After approval of Protocol Version 3.0, the collection of [EQ-5D](#), [EORTC QLQ-C30](#) and [EORTC QLQ LC-13](#) questionnaires will no longer be required.
10. See [Appendix 10.7](#): Adverse Event Reporting Process
12. Tumour assessments should include CT scans of the chest and abdomen and, if clinically indicated, imaging of any other known or suspected sites of disease (e.g. pelvis, brain) using an appropriate method (CT scan or MRI). See [Appendix 10.1](#) for lesion measurement specifications. Assessment will be performed at the following timepoints until progression or start of further treatment for disease. In the event of early discontinuation due to Adverse Events or an interruption/delay to treatment the tumour assessment schedule will not be changed.  
Screening Period (up to 21 days before randomization)  
During week 8 (56-64 days after randomization)

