### 5.3 OTHER

#### 5.3.1 Other endpoints

Patient-reported outcomes will be measured with the following multidimensional questionnaires included in [Appendix 10.8](#).

- [EQ-5D](#) health status self-assessment questionnaire ([R96-2382](#))
- EORTC QLQ-C30, European Organisation for Research and Treatment of Cancer (EORTC) Quality of Life Questionnaire ([QLQ-C30](#)) ([R99-1213](#), [R07-2064](#))
- EORTC Lung cancer specific supplementary module ([EORTC QLQ-LC13](#)) ([R07-2060](#), [R07-2065](#))

All three questionnaires will be completed at the time points specified in the Flow Chart. After approval of Protocol Version 3.0, the completion of [EQ-5D](#), [EORTC QLQ-C30](#) and [EORTC QLQ LC-13](#) questionnaires will no longer be required.

Questionnaires should be completed by patients prior to seeing the clinician, prior to clinical assessment, prior to any treatment at the clinic, and before provision of any new information about their disease status so that the responses are not influenced (biased). The questionnaires represent source documents. Validated translations exist for all questionnaires for all countries participating in the study and patients will receive the questionnaires in their native language.

Any unsolicited information provided by the patient on the questionnaire and any safety related data obtained from the patient's responses to the standard questions on the questionnaires will be immediately reported to the investigator. The investigator will review the patient's responses against the clinical assessment which corresponds to the timepoint the

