#### 6.2.2 Treatment period

*Course 1, Visit 1 (Day 1 of 1st treatment course)*

All procedures must be completed on Day 1 of Course 1. Refer to the flow chart for details.

Study medication must be administered as soon as possible after randomization, but within 2 days at the latest. Sites are strongly encouraged to have the patient take the first dose of study medication while he/she is still at the investigative site, and to document this in the site source documentation.

*Course 1, Visit 2 (8  $\pm$ 2 days after start of study drug)*

Refer to the flow chart for details.

*Course 2 (Day 1, -3 to +2 days) and all subsequent visits*

Refer to the flow chart for details.

In case a patient misses the scheduled study visit but reports to the investigative site before the next scheduled study visit, the missed visit should be performed. The current date and reason for the delayed visit should be noted in the source documentation. All subsequent study visits should take place at the start of the next treatment cycle per the flow chart. In the event of any study drug interruption or delay of treatment, the tumour assessment schedule will not be changed.

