6.7 BASELINE, TIME WINDOWS AND CALCULATED VISITS

Baseline values will be the measurements taken most recently prior to first administration of study drug.

Study day will be calculated relative to the date of the first administration of study drug. The day prior to first administration of study drug will be ‘Day -1’ and the day of first administration of study drug will be ‘Day 1’; therefore ‘Day 0’ will not exist.

For the presentation of tumour response data which will follow a calculated visit approach based on the protocol specified tumour imaging schedule. Imaging will be performed at week 8, 12 and 16, and in 8-weekly intervals thereafter from the date of randomisation; images will be slotted to Week 8, 12, 16, 24, ... XX based on their relative day and using a $\pm 2, \pm 4$ week window as appropriate (images taken in the first 4 weeks from randomisation will be slotted to Week 8). If two or more images for a patient are assigned to one interval then the last assessment will be used to ensure progressive disease is not missed. Note German sites only will have an X-ray completed instead of a CT or MRI for the week 12 assessment. If disease progression is suspected, a follow-up CT or MRI will then be completed. In the case where a CT or MRI is not completed for the week 12 assessment, it will be handled as missing assessment.

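### At sites that randomise ahead of C1V1, the only baseline HRQoL form follows open-label allocation, and the SAP accepts it as baseline

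*Protocol*

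**What the plan says.** **Timing of randomisation.** The flow chart marks randomisation at C1V1, but its footnote adds: "Randomization into the study via the IXRS is permitted up to 2 days prior to the C1V1 if site procedures require advance randomization". Sites that use the option must file their policy and send a copy to the sponsor.

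**Timing of the first form.** In the flow chart row "Patient-reported outcomes", the screening column is empty and the first mark is at C1V1. Footnote 9 says that the "questionnaires will be completed at baseline and then (before seen by the investigator) at the start of course 2, 3, 4", without relating the baseline form to randomisation. Protocol 6.2.2 says of C1V1: "All procedures must be completed on Day 1 of Course 1".

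**Order within the visit.** Protocol 5.3.1 says: "Questionnaires should be completed by patients prior to seeing the clinician, prior to clinical assessment, prior to any treatment at the clinic", and also before the patient hears anything new about disease status. The stated purpose is to avoid influencing the answers. Neither randomisation nor the treatment arm is in that list.

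**Masking.** Protocol 3.2 makes the trial open-label. The masking described covers the independent image readers and the sponsor's aggregate view, not patients or sites.

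**Analysis.** SAP 6.7 says: "Baseline values will be the measurements taken most recently prior to first administration of study drug". SAP 7.5.2.3 defines improvement and time to deterioration as changes of at least 10 points from baseline on a 0-100 scale. It also fits a growth curve to the scores over time.

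**The concern.** A baseline should be recorded before allocation can influence it. That is what makes a difference in change from baseline attributable to the randomised comparison. Self-reported cough, breathlessness and pain could shift once a patient knows whether the drug is the investigational one or the marketed comparator. In an open-label trial this cannot be prevented at later forms, but at baseline it can.

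The protocol already accepts the principle, since 5.3.1 keeps other influences away from the questionnaire. The gap is that a site following the plan exactly, under the advance option, obtains its baseline after allocation. No deviation is needed, and the SAP has no rule that would identify such a form. At stake is the reading of two HRQoL analyses that depend on a threshold change from that one form.

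**Working it through.** **1. Order of events.** Put C1V1 at day 0.
- Advance option: randomisation on day -2 or -1, baseline form on day 0, first dose after the form. Protocol 6.2.2 allows at most 2 days between randomisation and first dose, so this sequence complies.
- SAP 6.7: the form precedes first dose, so it counts as baseline.
- No earlier form exists to fall back on. The arm can therefore have been known for up to 2 days when the baseline is given.

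**2. Size of one answer.** The QLQ items concerned have responses 1 to 4. With linear scoring to 0-100 (assumed here; the SAP refers to the EORTC algorithm), moving one item by one category on a scale of k items changes the score by 100/(3k):

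| Scale | k | Step |
|---|---|---|
| Cough (Q31) and other single items (Q8, Q40, Q41, Q42) | 1 | 33.3 |
| Pain (Q9, Q19) | 2 | 16.7 |
| Dyspnoea (Q33, Q34, Q35) | 3 | 11.1 |

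Each step exceeds 10, so one category on one item is enough to cross the threshold.

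**3. What a shifted baseline does to one patient (cough).** Response 2 scores (2-1)/3 x 100 = 33.3; response 3 scores 66.7.
- Cough stays at 2, but 3 is recorded at baseline only: later change is 33.3 - 66.7 = -33.3, counted as improved. With 2 recorded at baseline the change is 0, counted as stable.
- Knowing the arm makes the patient answer 3 at baseline and at every later form: change from the C1V1 form is 0, counted as stable. Change from a form taken before randomisation (response 2) is +33.3, counted as worsened.

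The same reporting effect thus pushes the endpoint in different ways, depending on whether it fades or persists.

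**4. The same contrast in a whole arm.** These simulations of the cough item are illustrations, not estimates. They assume no true treatment effect, retest reliability 0.7, forms at weeks 4, 8, 12, 20 and every 8 weeks to week 52 while progression-free (exponential, median 10 weeks), 70% completion of the end-of-treatment and follow-up forms, and assumed response distributions.
- Shift at baseline only, one category worse in 5%, 10% or 20% of one arm: improved moves from 41.4% to 43.7%, 45.8% or 50.6%.
- Persistent shift in 10% of one arm, under three response distributions. With the form after allocation, improved moves from 40.4% to 40.0%, 44.3% to 43.5%, and 41.6% to 41.1%. With the form before randomisation it would be 37.1%, 41.3% and 38.0%.

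The sign and size follow from the assumptions, and the documents supply no basis for choosing among them.

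**5. The third analysis.** SAP 7.5.2.3 takes the area under the fitted curve, divides it by median follow-up and compares the resulting mean scores. It does not subtract baseline. The baseline form enters as one measurement among several.

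**The case against.** The strongest case on the other side has five parts.

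- **Few patients may be involved.** The option is conditional on site procedures, and its uptake is not stated. If 10% of an arm were randomised in advance (an assumption), shifting 5% of the arm would need half of those patients (0.10 x 0.5 = 0.05) to move a full category in the same direction. With 1-2% of an arm shifted at baseline only, improved moves by about 0.3 to 0.9 points. This stands as a limit on size.
- **Patients may not know their arm.** Site staff operate the IXRS, and the documents do not say that patients are told before C1V1. They do not say that the arm is withheld either. Site policies and further questionnaire instructions sit in the investigator site file, which is not part of these documents. This stands: knowledge is possible, not shown.
- **Same-day sites.** A reader might infer that every site is exposed, because no sentence puts the form before the IXRS call. But a form completed before seeing the clinician, as 5.3.1 asks, would normally precede same-day randomisation, since eligibility is also reviewed at C1V1. The exposure is essentially confined to advance-option sites.
- **A form after allocation may cancel a persistent reporting effect.** Step 4 shows that it can. It is not a reason to keep the arrangement: cancellation would occur only at some sites, by accident, and would leave two kinds of baseline in one analysis.
- **HRQoL is a supportive endpoint** outside the PFS-then-OS testing order. That lowers the priority of the point but does not remove it.

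**Conclusion.** The gap is real but narrow. At advance-option sites the plan as written produces a baseline HRQoL form after open-label allocation, and SAP 6.7 treats it as an ordinary baseline. Improvement and time to deterioration are directly exposed, because one altered answer (33.3, 16.7 or 11.1 points) exceeds the 10-point threshold.

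A reader might go further and conclude that all HRQoL results are biased in favour of one arm by a known amount. The documents do not support that. The growth-curve comparison is only indirectly affected, the number of patients concerned is not given, their knowledge of the arm is not stated, and direction and size depend on assumptions. PFS and OS are unaffected. This is a cheap improvement that removes an avoidable source of bias, not a threat to the trial's main conclusions. The score steps assume linear scoring of four-level items.

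**What to change.** - **Protocol, flow chart footnote 9 and Section 5.3.1:** state that the baseline questionnaires are completed before the IXRS randomisation call and before the arm is disclosed. Advance-option sites collect them shortly before that call, for example the same day or within a few days. The 28-day screening window is too loose: the QLQ-LC13 asks about the past week and the EQ-5D about the present day. Section 6.2.2 needs a matching exception to its Day 1 rule.
- **SAP 6.7:** define HRQoL baseline as the last form before randomisation.
- **Forms completed after randomisation:** compare form and randomisation dates, and times where recorded. Keep these patients in the main analysis, flag the form, report the counts by arm, and repeat the HRQoL analyses without those patients as a sensitivity analysis. Protocol Version 3.0 ends questionnaire collection, so for data already collected this is the part that can still be acted on. The policies sent to the sponsor should identify the sites.

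The cost is wording in three or four places and one sensitivity analysis. No form is added. The downside is that advance-option sites need the patient to complete the same form at a contact before randomisation rather than at C1V1.
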